7.6.3. Ninety (90) Days After the Last Dose of Study Medication

Subjects will have a visit 90 days after the last dose of any study medication (\pm 10 days). Efforts should be made to have subjects complete the 90-day post last treatment visit for safety evaluation. The visit is not necessary if the subject enrolls into another trial, if the subject begins treatment for the malignancy under study, or if hospice or palliative care is initiated before this visit; if possible, this visit should be scheduled earlier. Assessments are as indicated in Table 9.

7.6.4. Long-Term Follow-Up Period

All subjects will be followed for progression and OS approximately every 2 months (\pm 2 weeks) after the 90-day follow-up visit (see [Section 7.6.3](#)) visit. This includes subjects who discontinue treatment due to progression or toxicity, as well as those who discontinue before progression to pursue a new anti-lymphoma/salvage therapy (chemotherapy, SCT, radiotherapy, etc.). Subjects who discontinue due to toxicity and without progression will continue to have efficacy assessments performed until progression or the initiation of new therapy. Subjects will be contacted by telephone, email, or mail contact by the site until death or 5 years from randomization. The following data will be collected at each follow-up contact:

- Survival status date and cause of death (if applicable)
- Transplantation date and other transplant related outcomes (if applicable)
- Date of progression
- subsequent treatments and efficacy outcomes of those treatments
- date of last confirmation of survival (last know date alive)

It is anticipated that the information will be available from the treating Investigator, oncologist, primary care physician, local medical records, or the subject. The Investigator may search public sources for status information. Completion of the long-term follow-up period is required for any randomized subject, even if the subject did not receive the intervention. The duration of follow-up on this trial may be modified based on observed subject outcomes, ie, lengthened if significant numbers of durable responses are seen or shortened if few subjects require long follow-up.

7.7. Study Drug

7.7.1. Plamotamab (XmAb13676)

Plamotamab (XmAb13676) is a humanized bsAb that binds both CD3 and the tumor antigen CD20 in order to recruit cytotoxic T cells to kill CD20 positive tumor cells. IV Solution Stabilizer (IVSS) is a concentrated form of the plamotamab (XmAb13676) buffer that also minimizes protein binding to the administration equipment when plamotamab is administered at lower concentrations.

[REDACTED] Dilution instructions for any alternate fill volumes required during the study will be provided in the pharmacy manual.

[REDACTED]

7.7.2. Tafasitamab-cxix (Tafasitamab)

Tafasitamab-cxix (herein referred to as tafasitamab) for injection is supplied as a 200 mg vial containing a sterile, preservative-free, white to slightly yellowish lyophilized powder in a single-dose vial for IV use after reconstitution. After reconstitution with 5 mL of Sterile Water for Injection, USP, the resulting concentration is 40 mg/mL with a pH of 6.0. Each single-dose vial contains 200 mg tafasitamab, citric acid monohydrate (3.7 mg), polysorbate 20 (1 mg), sodium citrate dihydrate (31.6 mg) and trehalose dihydrate (378.3 mg).

7.7.3. Lenalidomide

Lenalidomide may be provided by the Investigator or as clinical trial material/investigational medicinal product (Revlimid or regionally approved generic lenalidomide).

7.8. Study Drug Storage

7.8.1. Plamotamab

Vials containing plamotamab and IVSS must be stored under refrigeration at [REDACTED] in an appropriately secured area accessible only to the pharmacist, the Investigator, or a duly designated person. Since plamotamab does not contain preservatives, opened vials of plamotamab must be used within 24 hours.

7.8.2. Tafasitamab

Vials containing tafasitamab are to be stored according to package insert or SmPC ([Monjuvi[®] PI, 2021](#); [Minjuvi[®] SmPC, 2021](#)).

7.8.3. Lenalidomide

Lenalidomide is to be stored according to the package label for Revlimid or generic lenalidomide (Revlimid[®] PI, 2021; Revlimid[®] SmPC, 2022).

7.9. Study Drug Preparation

7.9.1. Plamotamab

Note that plamotamab has pharmacodynamic effects in vivo at very low concentrations and therefore each product vial must be highly diluted before administration.

Plamotamab solution is prepared under aseptic conditions. Prior to administration, plamotamab will be diluted to the required final concentration in one or more infusion bags containing [REDACTED]. Prior to dilution, the vial containing parenteral drug product should be inspected visually. If particulate matter and/or discoloration are noted, drug should not be administered, and the Sponsor should be notified. After dilution, the bag containing plamotamab (XmAb13676) should be gently inverted 2 to 3 times to mix the solution. **THE BAG MUST NOT BE SHAKEN.** See the Study Pharmacy Manual for additional details.

7.9.2. Tafasitamab

Tafasitamab is prepared according to the package insert or SmPC (Monjuvi[®] PI, 2021; Minjuvi[®] SmPC, 2021).

7.9.3. Lenalidomide

Lenalidomide is provided as orally administered capsules, which the study center will dispense to the subject.

7.10. Study Drug Administration

7.10.1. Plamotamab

Plamotamab has previously been given to humans in a Phase 1 clinical study (XmAb13676-01). In the XmAb13676-01 study, CRS was frequently observed, especially with the Cycle 1 Day 1 dose (Section 2.4). Either a Principal Investigator or Sub-Investigator (MD) must be readily available during and for a minimum of 24 hours after administration of a plamotamab dose.

All subjects will be premedicated in Cycle 1 with dexamethasone 20 mg IV approximately 30 to 60 minutes prior to the start of the tafasitamab infusion. During Cycle 1, if tafasitamab infusion is held for any reason, dexamethasone will be given 1 hour prior to the start of the plamotamab administration. After Cycle 1, premedication with dexamethasone is not required and is permitted at the Investigator's discretion. (Cetirizine or other antihistamine may be used in place of diphenhydramine).

Plamotamab administration should begin as soon as possible after the dosing solution is prepared. If there is a delay in administration, it may be stored at [REDACTED].

Plamotamab SHOULD NOT BE ADMINISTERED AS AN IV PUSH OR BOLUS.

Study drug will be administered as an open-label solution at a [REDACTED] using a dedicated infusion set. Precautions for CRS or infusion reactions/anaphylaxis should be observed during plamotamab administration. Due to the possibility that CRS or allergic/infusion reactions may occur, emergency resuscitation equipment (a “crash cart”) and medications including steroids and tocilizumab should be present in the immediate area where subjects are receiving their infusions. Additional supportive measures should be available and may include, but are not limited to, acetaminophen, antihistamines, corticosteroids, IV fluids, bronchodilators, epinephrine, vasopressors, and oxygen.

Management of CRS and other infusion-related reactions will be per standard investigational site procedures, or alternatively, as outlined in this protocol. Please refer to [Section 4.6](#) for management of infusion reactions/CRS and neurotoxicity, if needed.

Vital signs will be measured and recorded as described in [Section 7.6.1](#).

7.10.2. Tafasitamab

Tafasitamab will be administered according to the package insert or SmPC ([Monjuvi[®] PI, 2021](#); [Minjuvi[®] SmPC, 2021](#)).

7.10.3. Lenalidomide

Lenalidomide will be dispensed to the subject to take orally in the evening according to the package insert or SmPC ([Revlimid[®] PI, 2021](#); [Revlimid[®] SmPC, 2022](#)). The subject will be given a diary to record the date and time of each administration of lenalidomide and to provide accountability of the product.

If a subject misses a dose of lenalidomide and it is within 12 hours of their normal dosing time, the subject should be instructed to make up the missed dose, and to then take their next dose according to their regular schedule.

7.11. Study Drug Accountability, Handling, and Disposal

Detailed instructions and procedures for study drug dispensing are included in the Pharmacy Manual.

Accurate accounting of all study medication must be maintained. The Investigator agrees to keep an inventory of study drugs using local investigational pharmacy drug accountability logs. Drug disposition records must be kept in compliance with applicable guidelines and regulations.

Upon completion or termination of the study, any used vials, partially used vials, unused study medication, unused diluted drug dosing solutions, or unused IVSS should be destroyed in

Any unused lenalidomide must be returned to the study center for accountability and destruction according to local regulations or institutional policy.

Subjects will be required to keep a diary of the administration of lenalidomide. Dosing instructions will be provided to the subject. Compliance with study intervention will be assessed at the beginning of each cycle. Compliance will be assessed by counting returned capsules, in conjunction with subject diary information and subject questioning and counseling during the site visits and documented in the source documents and eCRF. Deviation(s) from the prescribed dosage regimen should be recorded in the eCRF.

A record of the number of lenalidomide capsules dispensed to and taken by each subject must be maintained and reconciled with study medication and compliance records. Lenalidomide start and stop dates, including dates due to delays and/or dose reductions, will also be recorded in the eCRF.

8. PHARMACOKINETIC, PHARMACODYNAMIC, AND BIOMARKER ASSESSMENTS

8.1. Serum Assessments for Pharmacokinetic Analyses, Anti-Drug Antibodies, Cytokines, and Rituximab Levels

Venous blood samples for serum analyses of plamotamab and tafasitamab PK, plamotamab and tafasitamab ADA, cytokines, and rituximab levels will be obtained as per the schedule listed in [Table 10](#) and [Table 11](#). Remaining samples will be stored for additional testing of biomarkers associated with pharmacodynamic activity, clinical response, or resistance to the study drugs. This testing may occur at ICON Laboratory Services, Inc. or at another Sponsor designee as detailed in the Laboratory Manual.

8.2. Pharmacodynamics and Biomarker Assessments

8.2.1. Peripheral Blood Assessments

Blood specimens will be collected to explore pharmacodynamic effects of plamotamab, tafasitamab, and lenalidomide on leukocyte frequencies and markers of T-cell and/or leukocyte function, including, but not limited to, checkpoint molecules, markers of proliferation and T-cell activation, and markers of T-cell exhaustion. The frequencies of circulating T cells, B cells and NK cells will also be monitored. Additional blood samples will be drawn into PAXgene RNA tubes and stored for potential explorative studies of leukocyte function and pharmacodynamic effects by RNA sequencing and transcriptomic gene and pathway analysis. Baseline and pharmacodynamic markers in the periphery will be evaluated for correlation with incidence of CRS and AEs along with clinical response and resistance. Assessment of CRS in the 24 hours following each dose will include monitoring serum cytokines and flow cytometric evaluation of the change in the quantity and activation state of T cells in the peripheral blood.

A blood sample will be collected at screening and on treatment for measurement of ctDNA. By tracking levels of and mutations in ctDNA by DNA sequencing methods on treatment, ctDNA as a

measure of MRD will be explored as a marker of clinical response. Blood samples may also be used to evaluate germline DNA variation across the genome in order to interpret tumor-specific DNA mutations.

Detailed instructions for processing and shipping peripheral blood samples are provided in the Laboratory Manual. For the sampling schedule, see [Table 9](#) (Schedule of Assessments). Unscheduled samples may be collected and sent to the designated central laboratory at the discretion of the Investigator. Remaining peripheral blood mononuclear cells, plasma samples, and serum samples will be stored at the designated central laboratory and may be used for assessment of additional future exploratory biomarkers associated with pharmacodynamic activity, clinical response, or resistance to the study drugs.

8.2.2. Tumor Biopsies

8.2.2.1. Archival Tissue

Archival blocks (preferred) or unstained slides will be requested from lymph node biopsies to confirm DLBCL diagnosis, determine cell of origin status, and to perform genomic mutation analysis. Cell of origin assays (COO), germinal center B-cell (GCB), or activated B cell type (ABC) origin will be determined using transcriptional analysis, Nanostring LymphC2x, or other gene expression methods. Immunohistochemistry analysis will be performed using relevant markers in the Hans algorithm ([Yoon, 2017](#)).

Archival tissues of diagnostic tumor mass or lymph node must be confirmed to be available at the time of study entry and will be collected and sent to the designated central laboratory within 8 weeks of first dose of study medication or randomization. For the sampling schedule, see [Table 9](#) (Schedule of Assessments). If archival tissue is not available, a fresh tumor biopsy at baseline will be requested ([Section 8.2.2.2](#)).

8.2.2.2. Baseline and On-Treatment Tumor Biopsies

Baseline Biopsies: Fresh tumor biopsies (excisional or core needle biopsies) are encouraged as they allow an unbiased analysis of tumor status in contrast to archival biopsies which may not reflect impact of therapies prior to study start. Therefore, pretreatment baseline biopsies will be requested if the subject provides consent and presents with accessible involved lymph nodes, for instance, superficial lymphadenopathy, enabling low-risk procedures to be performed to obtain tissue. Excisional or core needle biopsies are acceptable while fine needle aspiration is not acceptable.

On-treatment Biopsies: On-treatment biopsies are requested in subjects with accessible lymphadenopathy. On-treatment biopsies are to be obtained in the fourth week of treatment (after the C1D22 dose, but prior to the C2D1 dose). In responding subjects, an additional biopsy is recommended upon progression to ascertain the molecular and cellular basis of progression, and to specifically rule out loss of CD19 or CD20 expression as a mechanism of acquired resistance.

Tumor tissue from archival, pretreatment, on-treatment and progression biopsies will be processed to enable analysis, including, but not limited to, (1) DNA sequencing to identify acquired genetic

variants in tumor cells; (2) RNA analysis of tumor and the tumor microenvironment; (3) immunostaining of the tumor for CD19 and CD20 expression, and of the inflammatory cells, including T cells, in the microenvironment.

Baseline and on-treatment biopsies will be collected and sent to the central laboratory designated in the Laboratory Manual. For the sampling schedule, see [Table 9](#) (Schedule of Assessments).

Following the study specified tumor biopsy analysis, remaining archival and fresh biopsy samples will be stored at the designated central laboratory for assessment of additional future exploratory biomarkers associated with pharmacodynamic activity, clinical response, or resistance to the study drugs.

9. ASSESSMENT OF EFFICACY

9.1. Efficacy Assessments

Table 16: Assessment of Response

Response	Site	PET-CT–Based Response	CT-Based Response
Complete	Lymph nodes and extralymphatic sites	Complete metabolic response Score 1, 2, or 3 ^a with or without a residual mass on 5PS ^b	Complete radiologic response (all of the following) Target nodes/nodal masses must regress to < 1.5 cm in LDi No extralymphatic sites of disease
	Nonmeasured lesion	Not applicable	Absent
	Organ enlargement	Not applicable	Regress to normal
	New lesions	None	None
	Bone marrow	No evidence of FDG-avid disease in marrow	Normal by morphology; if indeterminate, IHC negative
Partial	Lymph nodes and extralymphatic sites	Partial metabolic response Score 4 or 5 ^b with reduced uptake compared with baseline and residual mass(es) of any size	Partial remission (all of the following) > 50% decrease in SPD of up to 6 target measurable nodes and extranodal sites When a lesion is too small to measure on CT, assign 5 mm × 5 mm as the default value When no longer visible, 0 × 0 mm For a node > 5 mm × 5 mm, but smaller than normal, use actual measurement for calculation
	Non-measured lesion	Not applicable	Absent/normal, regressed, but no increase
	Organ enlargement	Not applicable	Spleen must have regressed by > 50% in length beyond normal
	New lesions	None	None
	Bone marrow	Residual uptake higher than uptake in normal marrow but reduced compared with baseline (diffuse uptake compatible with reactive changes from chemotherapy allowed). If there are persistent focal changes in the marrow in the context of a nodal response, consideration should be given to further evaluation with MRI or biopsy or an interval scan	Not applicable

Table 16: Assessment of Response (Continued)

Response	Site	PET-CT–Based Response	CT-Based Response
Stable or No response	Target nodes/nodal masses, extranodal lesions	No metabolic response Score 4 or 5 with no significant change in FDG uptake from baseline at interim or end of treatment	Stable disease < 50% decrease from baseline in SPD of up to 6 dominant, measurable nodes and extranodal sites; no criteria for progressive disease are met
	Non-measured lesion	Not applicable	No increase consistent with progression
	Organ enlargement	Not applicable	No increase consistent with progression
	New lesions	None	None
	Bone marrow	No change from baseline	Not applicable
Progressive	Individual target nodes/nodal masses Extranodal lesions	Progressive metabolic disease Score 4 or 5 with an increase in intensity of uptake from baseline and/or New FDG-avid foci consistent with lymphoma at interim or end-of-treatment assessment	Progressive disease requires at least 1 of the following PPD progression: An individual node/lesion must be abnormal with: LDi > 1.5 cm and Increase by > 50% from PPD nadir and An increase in LDi or SDi from nadir 0.5 cm for lesions ≤ 2 cm 1.0 cm for lesions > 2 cm In the setting of splenomegaly, the splenic length must increase by > 50% of the extent of its prior increase beyond baseline (eg, a 15-cm spleen must increase to > 16 cm). If no prior splenomegaly, must increase by at least 2 cm from baseline New or recurrent splenomegaly
	Non-measured lesions	None	New or clear progression of preexisting non-measured lesions

Response	Site	PET-CT-Based Response	CT-Based Response
	New lesions	New FDG-avid foci consistent with lymphoma rather than another etiology (eg, infection, inflammation). If uncertain regarding etiology of new lesions, biopsy or interval scan may be considered	Regrowth of previously resolved lesions A new node > 1.5 cm in any axis A new extranodal site > 1.0 cm in any axis; if < 1.0 cm in any axis, its presence must be unequivocal and must be attributable to lymphoma Assessable disease of any size unequivocally attributable to lymphoma
	Bone marrow	New or recurrent FDG-avid foci	New or recurrent involvement

5PS = 5-point scale; CT = computed tomography; FDG = fluorodeoxyglucose; IHC = immunohistochemistry; LDi = longest transverse diameter of a lesion; MRI = magnetic resonance imaging; PET = positron emission tomography; PPD = cross product of the LDi and perpendicular diameter; SDi = shortest axis perpendicular to the LDi = SPD, sum of the product of the perpendicular diameters for multiple lesions.

Measured dominant lesions: Up to six of the largest dominant nodes, nodal masses, and extranodal lesions selected to be clearly measurable in two diameters. Nodes should preferably be from disparate regions of the body and should include, where applicable, mediastinal and retroperitoneal areas. Non-nodal lesions include those in solid organs (eg, liver, spleen, kidneys, lungs), GI involvement, cutaneous lesions, or those noted on palpation. Recently biopsied lesions should not be used as a measured dominant lesion.

Nonmeasured lesions: Any disease not selected as measured, dominant disease and truly assessable disease should be considered not measured. These sites include any nodes, nodal masses, and extranodal sites not selected as dominant or measurable or that do not meet the requirements for measurability but are still considered abnormal, as well as truly assessable disease, which is any site of suspected disease that would be difficult to follow quantitatively with measurement, including pleural effusions, ascites, bone lesions, leptomeningeal disease, abdominal masses, and other lesions that cannot be confirmed and followed by imaging.

- ^a In Waldeyer’s ring or in extranodal sites (eg, GI tract, liver, bone marrow), FDG uptake may be greater than in the mediastinum with complete metabolic response but should be no higher than surrounding normal physiologic uptake (eg, with marrow activation as a result of chemotherapy or myeloid growth factors).
- ^b PET 5PS: 1, no uptake above background; 2, uptake ≤ mediastinum; 3, uptake > mediastinum but ≤ liver; 4, uptake moderately > liver; 5, uptake markedly higher than liver and/or new lesions; X, new areas of uptake unlikely to be related to lymphoma.

The Investigator and the BIRC will assess response to study drug at each efficacy timepoint. The following endpoints will be reported:

Progression-free Survival: defined as the time from randomization to the first documentation of progressive disease or death, whichever comes first. The Investigator and the BIRC will determine the progressive disease event in all randomized subjects.

Duration of Response: defined as the time from the first response (CR or PR) to progression or death due to any cause among subjects achieving a CR or PR and among CR subjects. DOR will be derived using disease progression as determined by the BIRC in subjects who have a response (CR or PR).

Overall Survival: defined as the time from randomization to death from any cause. All randomized subjects will be followed for up to 5 years for survival.

Time to Treatment Failure: defined as the time from randomization to discontinuation of all study treatment for any reason, including disease progression, treatment toxicity, and death. The time to treatment failure will be using disease progression as determined by the Investigator and by the BIRC.

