4.2.2. Secondary Endpoints

The secondary endpoints of the study are as follows:

1. Best ORR and CRR, as assessed by Investigator and by the BIRC according to Lugano 2014 criteria (Cheson, 2014)

2. OS, defined as the time from randomization to death from any cause
3. TTF, defined as the time from randomization to discontinuation of all study treatment for any reason, including disease progression (as assessed by Investigator and by BIRC), treatment toxicity, and death, whichever comes first
4. DOR, defined as the time from first response to progression or death due to any cause, whichever comes first, among subjects achieving an objective response (OR) and among subjects with CR as assessed by BIRC
5. PFS, as assessed by Investigator using Lugano 2014 criteria
6. Incidence, timing, and severity of CRS as assessed by following CRS-related AEs, including incidence and grade of AEs and incidence of SAEs, with CRS grading defined by the ASTCT Consensus Grading
7. Incidence, timing, and severity of neurological AEs, and incidence and grade of Immune Effector Cell-Associated Neurotoxicity Syndrome (ICANS)
8. Dose intensity of tafasitamab and lenalidomide as measured by planned and actual dose administration in Part 1
9. Incidence and severity of TEAEs in Part 2, with severity defined by the National Cancer Institute (NCI)-Common Terminology Criteria for Adverse Events (CTCAE) version 5.0

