4.3.1. Part 1: Single-Arm, Safety Run-In

Part 1 is a single-arm, two-cohort, safety run-in intended to establish the safety of the combination of plamotamab, tafasitamab, and lenalidomide.

Treatment consists of the combination of plamotamab, tafasitamab, and lenalidomide administered in 28-day cycles, with 2 priming doses of tafasitamab before Cycle 1. Plamotamab and tafasitamab can be administered until disease progression, unacceptable toxicity, or discontinuation for any other reason, whichever comes first; however, lenalidomide can be given for only up to a total of 12 cycles. Tafasitamab and plamotamab must not be administered simultaneously. On days when both tafasitamab and plamotamab are given, the tafasitamab should be given first followed by plamotamab. It is recommended that the infusions are separated by at least 2 hours.

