- ^q PET/CT and bone marrow biopsy/aspirate (for subjects with known bone marrow involvement). All studies for the baseline assessment should be performed within 21 days prior to Day -8. After Cycle 12, perform disease assessments every 3 cycles (or Q12 weeks) up to Cycle 36 and every 4 cycles (Q16 weeks) up to Cycle 60. Any unscheduled disease assessment performed in suspicion of progressive disease must be recorded in the eCRF.
- ^r PHI-redacted tumor assessments including, but not limited to assessment reports and/or digital imaging files (DICOM) for scans/imaging, blood, and bone marrow biopsy pathology reports are to be provided to support response assessments.
- ^s Archival tissue from excisional biopsies of lymph node to be sent to the designated central laboratory as an archival block (**preferred**) or up to 43, if possible, unstained slides. Archival tissue must predate study treatment. If archival tissue is not available or is insufficient, the screening fresh tumor biopsy becomes mandatory to satisfy the inclusion criterion.
- ^t Fresh tumor biopsy will be collected at screening up to 21 days prior to Day -8. The on treatment fresh tumor biopsy performed after the fourth dose between the C1D22 and C2D1 visit. Fresh tumor biopsy is strongly encouraged but is optional and requires separate consent. The baseline sample becomes mandatory for study participation if archival tissue is not available to satisfy the inclusion criterion.
- ^u The Screening (baseline) sample will come from the submitted archival or fresh tumor biopsy sample to identify malignant clones. Samples of whole blood and plasma will be collected through C2D1; only whole blood will be collected at C2D26, C6D1, C9D1, C12D1 and EOT for the detection and quantification of ID clonotype(s) that were identified from the baseline sample.

- ^v Male subjects will be followed for 6 months, and female subjects 8 months following the last dose of study drug to confirm contraceptive use.
- ^w Subjects who complete a tumor assessment within the prior 14 days do not have to repeat the EOT tumor assessment. If a subject was removed from study for disease progression and this response data for that applicable visit is adequately documented in EDC, the post-treatment (EOT and 90 days post EOT) tumor assessments do not need to be repeated.
- ^x Treatment-related SAEs should be followed up until resolution.

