 - For plamotamab infusion, vital signs and clinical assessment for AEs are monitored for a minimum of 5 hours after the end of the infusion. Timepoints include: predose; approximately 15, 30, and 60 minutes after start of plamotamab infusion (\pm 5 minutes); at end of infusion (\pm 5 minutes); approximately 15 (\pm 5) minutes; 30 (\pm 5) minutes; 60 (\pm 10) minutes after EOI; and then hourly for 4 additional hours (all windows \pm 15 minutes). The pulse oximetry for blood oxygen saturation level needs to be recorded with each vital sign collection; however, pulse oximetry monitoring must be maintained continuously, as practical, throughout the entire admission period for each administration of plamotamab, regardless of inpatient or outpatient status. For subjects who tolerate 4 consecutive infusions of plamotamab at a stable dose and schedule without CRS or an infusion reaction during the infusion or post-infusion observation period, the post-infusion observation period and vital signs assessment may be reduced from 5 hours to 2 hours.
- ECOG performance status (see Appendix A, Performance Status Scale).
- Supine ECG, standard 12-lead (see the Schedule of Assessments [Table 9] for timing of collections, and as clinically indicated). Triplicate ECG at C1D1 only, prior to the Plamotamab infusion. All ECG tracings will be submitted electronically to the Sponsor either by file transfer or scanning the original tracing. Additional details will be provided in a separate manual.
- Lenalidomide Counseling is performed on Day 1 of each cycle. Please see the supplemental Summary of Pregnancy Prevention Strategies, provided under separate cover, for details.

- Record concomitant medications
- Record AEs (CTCAE and CRS revised grading system)
- Tumor assessments will be performed as outlined in [Section 9](#) after Cycle 2, then at the end of even-numbered cycles up to Cycle 12, then every 3 cycles up to Cycle 36, and then every 4 cycles up to Cycle 60, and at EOT.

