3. TTF

Other secondary efficacy endpoints will be assessed, including:

- PFS, as assessed by Investigator
- ORR by Investigator
- DOR among subjects achieving an objective response
- DOR among subjects achieving a CR

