In addition to BIRC response assessments, Investigator-assessed responses will be reported similarly, and concordance analyses will be detailed in the SAP.

The duration of objective response will be calculated from the time of initial response (PR or better) to the first documentation of relapse (recurrence after CR), progression, or death. The duration of complete response will be calculated from the time of initial response (CR) to the first documentation of relapse (recurrence after CR), progression, or death among subjects achieving a CR.

Time to event analysis of OS, measured relative to randomization, will be performed based on the Kaplan-Meier method. Median survival time and its 95% confidence interval, as well as the 25th and 75th quartiles with their 95% confidence intervals, will be summarized. Subjects who are alive at end of the study will be censored at last known contact date. By-arm comparisons will utilize the same methods as for PFS.

The potential antitumor effects of plamotamab may be evaluated in subgroups of subjects, including the Key Subgroups defined in [Section 11.6](#). The specifications for these and other similar analyses will be described in the SAP, which supersedes any protocol specifications.

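### Duration of response among complete responders starts at the first CR or PR in Protocol 9.1 but at the first CR in 11.9, and the 9.1 start adds event-free time for subjects who move from PR to CR

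*Protocol*

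**What the plan says.** - **Protocol 9.1** gives one definition for both populations: time from "first response (CR or PR) to progression or death due to any cause among subjects achieving a CR or PR and among CR subjects".
- **Protocol 4.2.2** reads "DOR, defined as the time from first response to progression or death due to any cause, whichever comes first", applied to objective responders and to complete responders as assessed by the BIRC. Both endpoint lists in the synopsis and SAP 2.4.2 give the same definition. None of these says whether first response means first CR for the complete-responder group.
- **Protocol 11.9** has two rules. For all responders: "The duration of objective response will be calculated from the time of initial response (PR or better"). For complete responders: "The duration of complete response will be calculated from the time of initial response (CR) to the first documentation of relapse", progression or death.
- **Protocol 11.3.4** lists one duration endpoint for complete responders among the other secondary efficacy endpoints: "DOR among subjects achieving a CR".
- **SAP** sections 1, 4.1 and 7 state that the sponsor ended the study early with 3 subjects enrolled. No efficacy analysis will be run, but efficacy listings will be produced. The SAP contains no DOR derivation beyond the endpoint definition.

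**The concern.** One named secondary endpoint has two starting points. They agree for a subject whose first response is a CR and disagree for a subject whose first response is a PR that later becomes a CR.

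The 9.1 start also has a structural fault. Membership of the complete-responder group is decided by an event that comes after the clock has started. A partial responder who progresses or dies before reaching CR never enters the group. Every converter therefore brings a PR-to-CR interval in which failure was impossible, and that interval is counted as duration. The reported durability of complete responses is lengthened by an amount that depends on how many subjects convert and how late.

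**Working it through.** The documents give no sample size, power or event count for DOR, so there is no planned figure to reproduce. The check is a comparison of the definitions, followed by the size of the gap.

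**Clock start for complete responders, by section**

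| Place | Start |
|---|---|
| Synopsis (two lists), Protocol 4.2.2, SAP 2.4.2 | First response, type not stated |
| Protocol 9.1 | First CR or PR |
| Protocol 11.9 | First CR |

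**Inputs from the documents**
- Cycle length: treatment is "administered in 28-day cycles" (Protocol 4.3.1; the same length applies in Part 2 under 4.3.2).
- Scans: "after Cycle 2, then at the end of even-numbered cycles up to Cycle 12" (Protocol 7.6.1).
- Later scans: "After Cycle 12, perform disease assessments every 3 cycles (or Q12 weeks) up to Cycle 36", then every 16 weeks up to Cycle 60 (Protocol Section 5, notes to Table 9).

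**Inputs not in the documents (assumptions)**
- Share of complete responders who first had a PR: 20% to 50%.
- Delay from PR to CR: one or two scheduled scans.

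**Gap per converter** (1 month = 365.25 / 12 = 30.44 days)
- One scan step up to Cycle 12: 2 × 28 = 56 days; 56 / 30.44 = 1.84 months.
- PR at Cycle 2, CR at Cycle 6: 112 days = 3.68 months.
- Extreme case, PR at Cycle 2, CR at Cycle 12: 280 days = 9.2 months.
- After Cycle 12, one step is 84 days (2.76 months) or 112 days (3.68 months).

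These gaps are nominal. Scans fall on Day 26 ± 3, so a 56-day step could be 50 to 62 days (1.64 to 2.04 months), and unscheduled scans could change it further.

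**One subject under both rules.** PR at the end of Cycle 2, CR at the end of Cycle 4, progression at the end of Cycle 12. Protocol 9.1 gives 10 × 28 = 280 days (9.2 months). Protocol 11.9 gives 8 × 28 = 224 days (7.4 months). The 56-day difference is the PR-to-CR interval.

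**Effect on the group mean** = converter share × gap
- Low: 0.20 × 1.84 = 0.37 months.
- High: 0.50 × 3.68 = 1.84 months.

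**Effect on the median.** The protocol summarises time-to-event endpoints by Kaplan-Meier medians, so the shift was also simulated. Duration from first CR was taken as exponential with assumed medians of 12, 24 and 43.9 months. The last is the median DOR that Protocol 3.4 quotes for all responders to the control regimen, used here only as an upper value. Over the same range of shares and gaps, the median rose by 0.37 to 1.94 months.

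With the clock started at first CR, the guaranteed event-free time is zero.

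**The case against.** The strongest reply is that 11.9 already contains the right rule, in the section that governs efficacy analysis, under the label of duration of complete response. On that view 9.1 is loose shorthand, or the two sections describe different quantities. This stands in part: the rule needed is already written. But 11.3.4 lists only one complete-responder duration endpoint, 11.9 offers no other calculation for it, and nothing names a second quantity. The two sections therefore still conflict.

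Three stronger readings are tempting, and the documents do not support them.

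- **That all the endpoint sections and the SAP adopt the 9.1 start.** Only 9.1 spells out CR or PR in the definition. The synopsis, 4.2.2 and SAP 2.4.2 could be read as the first response of the relevant type, which would agree with 11.9. They are ambiguous, not contradictory.
- **That the arms will be compared on unequal quantities.** Different conversion rates would distort such a comparison in principle. With 50% and 20% conversion and the same 24-month median from CR, the simulated medians differ by 0.58 months (56-day gap) or 1.17 months (112-day gap). But Part 2 was to follow a safety evaluation of at least 40 Part 1 subjects, only 3 subjects were enrolled, and the SAP plans no efficacy analysis. DOR also lies outside the tested sequence (ORR, OS, TTF), so no formal claim rests on it. And DOR among responders conditions on response after randomization under either clock, so the first-CR start would not make it a randomized comparison.
- **That the inflation has a known size.** The converter share and the delay are assumptions, and the 9.2-month figure is a single extreme pattern.

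**Conclusion.** The inconsistency between Protocol 9.1 and 11.9 is real, and the other definitions do not resolve it. The 9.1 start biases the complete-responder duration upward, because converters are credited with time in which they could not fail. That conclusion assumes that a CR recorded after progression does not count. The protocol does not say so outright, but it follows from ending DOR at progression.

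For each converter the excess is nominally at least 56 days at scheduled scans up to Cycle 12. For the group it is about 0.4 to 1.8 months on the mean, resting wholly on the assumed 20% to 50% conversion after one or two scans. Against the 43.9-month median DOR quoted in Protocol 3.4 for all responders to the control regimen, that is roughly 1% to 4% (0.37 / 43.9 and 1.84 / 43.9).

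The practical impact is minor. What remains is the definition of a planned secondary endpoint, and the start date of any derived DOR in the efficacy listings. The SAP does not say whether those listings will show one.

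**What to change.** Use one clock for each population throughout:

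- DOR among all responders starts at the first CR or PR.
- DOR among complete responders starts at the first documented CR, as 11.9 already has it.

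Align five places: both endpoint lists in the synopsis, Protocol 4.2.2, Protocol 9.1 and SAP 2.4.2. If time from first response in subjects who reach CR is also wanted, give it its own name and report it separately. If the efficacy listings show a derived DOR, state the start date used.

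The cost is wording only. No new data are needed, and the complete-responder duration becomes slightly shorter wherever there are converters.
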